8.4.1 Hematology

Hematology includes assessment of Complete Blood Count (CBC) including: hemoglobin, white blood cell count, platelet count, and a differential count including: neutrophils, lymphocytes, monocytes, eosinophils, and basophils. Hematological evaluations (CBC) should be collected according to the Visit Schedule (see [Table 2](#)).

8.4.2 Biochemistry

The following blood chemistry results should therefore be collected according to the Visit Schedule (see [Table 2](#)).

Serum Creatinine, Bun, Glucose, Sodium, Potassium, Total Protein, Albumin, SGOT (AST), SGPT (ALT), Alkaline Phosphatase, and Total Bilirubin.

When, in the opinion of the investigator, other clinical laboratory evaluations may be relevant for assessing the patient's status, they will be completed and entered into the database as appropriate.

8.4.3 Special tests:

N/A

8.4.4 Urinalysis

Urinalysis will be performed according to the visit schedule (see [Table 2](#)). Specific gravity, pH, semi-quantitative “dipstick” evaluation of glucose, protein, bilirubin, ketones, leukocytes and blood. In case of findings on the urinary dipstick, such as leukocytes, nitrites or blood (except during menstruation for the female subjects), a microscopic examination including RBC/HPF, WBC/HPF and casts/LPF will be performed. If casts are noted, the type is to be specified on the relevant comments page in the CRF. A midstream urine sample (~ 30 mL) will be obtained, in order to avoid contamination and allow a proper assessment.

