2.3 Investigational product

Empagliflozin (Jardiance®) is indicated as an adjunct to diet and exercise to improve glycemic control in adults with type 2 diabetes mellitus.

Empagliflozin is an orally-active inhibitor of the sodium-glucose co-transporter 2 (SGLT2).

The chemical name of empagliflozin is D-Glucitol,1,5-anhydro-1-C-[4-chloro-3-[[4- [[(3S)-tetrahydro-3-furanyl]oxy]phenyl]methyl]phenyl]-, (1S).

Its molecular formula is $C_{23}H_{27}ClO_7$ and the molecular weight is 450.91.

Mechanism of action: Sodium-glucose co-transporter 2 (SGLT2) is the predominant transporter responsible for reabsorption of glucose from the glomerular filtrate back into the circulation. Empagliflozin is an inhibitor of SGLT2. By inhibiting SGLT2, empagliflozin reduces renal reabsorption of filtered glucose and lowers the renal threshold for glucose, and thereby increases urinary glucose excretion.

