4.2.1 Visit schedule and assessments

Table 2 visit schedule and assessments

Trial Period	Screening	Treatment Period			
Visit	1	2	3	4	5
Study Week	0	8	16	20	28
Days from randomization	-56	0	56	84	140
Informed Consent	X				
Inclusion/Exclusion Criteria	X	X			
Medical History	X				
Concomitant therapy	X	X	X	X	X
Demographics	X				
Physical Exam	X	X			
Vital Signs	X	X	X	X	X
Height	X				
Weight	X	X	X	X	X
Randomization		X			
Pregnancy test ¹	X	X		X	X
Home Blood glucose monitoring ²		X	X	X	X
Safety blood samples ³	X	X	X		X
HbA _{1c}	X		X		X
Device Interrogation	X	X	X	X	X
Monitor Counter Reset	X	X	X	X	X
12 Lead Holter ECG for 24hrs		X	X		X
Echocardiography	X ⁴	X	X		X
NT-Pro-BNP		X	X	X	X
Medication Compliance check			X		X

¹ For female patients with childbearing potential (Urine pregnancy test).

[figure not shown]
² Patients without means for daily home blood glucose monitoring will be given a device on visit 2. Glucose level will be measured 3 times a day in the first week and thereafter once a week or as needed. Additional measurements are warranted in the case of hypo- or hyperglycemia signs or symptoms.

³ Safety blood samples include: Fasting blood samples (8hr fasting), Liver and kidney functions, urine dipstick for signs of infection and ketoacidosis (if positive leukocyte esterase (WBC) or nitrites a midstream urine sample for urine culture will be taken.

⁴ Echocardiography will be done if needed to verify patient suitability for inclusion criteria.

Trial Period	Screening	Treatment Period			
Visit	1	2	3	4	5
Study Week	0	8	16	20	28
Days from randomization	-56	0	56	84	140
Endocrinologist consult		X			
Biobank samples		X	X	X	X
Urine Analysis (Electrolytes)		X	X	X	X
24hr Urine Sample collection		X	X	X	X
CardioPulmonary Exercise Test & 6 minute walk distance ⁵		X	X		X
Adverse events		X	X	X	X

Study scheme

Visit 3
Analysis 1

Visit 5
Analysis 2

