Treatment washout visit (3) (day 56 ±7 days)

1. Provide patient with 30 tablets of study drug for home use
2. Collect study drug blisters returned by patient.
3. Measure vital signs in order to ensure compliance with study criteria. Vital signs measurements will include systolic and diastolic blood pressure, pulse rate, respiratory rate, and body temperature. Body weight will also be measured.
4. Collect safety blood and urine samples. Including hematology and chemistry blood examinations and urine dipstick for signs of ketoacidosis or infection.
5. Remind patient to follow the endocrinologist instructions given on visit 2.
6. Collect venous blood that will be drawn for HbA1c.
7. Collect home diary glucose results and provide a new diary for the following period.
8. Perform device interrogation.
9. Perform Monitor counter reset.
10. Collect Holter ECG device results and invite study subject to study site for Holter ECG installation in one of the 7 days days before the next visit.
11. Perform echocardiography for determination of EF
12. Collect blood examination for NT-Pro-BNP
13. Collect urine and blood examination for biobank sample
14. Collect urine for electrolyte concentration
15. Obtain 24 hours urine sample collection
16. Perform cardiopulmonary exercise test (In case of inability to perform cardiopulmonary exercise test according to clinical judgment , patient will have a 6 minute walk distance test)

17. Perform 6 minute walk distance
18. Review concomitant medications.
19. Document adverse events.

Treatment visit (4) (day 84 ±7 days)

1. Provide patient with 60 tablets of study drug for home use
2. Collect study drug blisters returned by patient.
3. Measure vital signs in order to ensure compliance with study criteria. Vital signs measurements will include systolic and diastolic blood pressure, pulse rate, respiratory rate, and body temperature. Body weight will also be measured.
4. Review menopausal status and in women of childbearing potential perform a urine pregnancy test (β -HCG).
5. Remind patient to follow the endocrinologist instructions given on visit 2.
6. Collect home diary glucose results and provide a new diary for the following period.
7. Perform device interrogation.
8. Perform Monitor counter reset.
9. Collect blood examination for NT-Pro-BNP
10. Collect urine and blood examination for biobank sample
11. Collect urine for electrolyte concentration
12. Obtain 24 hours urine sample collection
13. Review concomitant medications

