4.3.2 Treatment assignment

Treatment assignment will take place only after getting patients' Informed consent and determining patient's eligibility. Each patient will be assigned a unique patient number. Once assigned, numbers for any non-evaluable or discontinued patient will not be reused.

A central randomization based on a 1:1 basis, of a pre-determined randomization schedule prepared by the data management of the CRO will provide the investigator treatment allocation to empagliflozin or placebo by fax or email. Treatment allocation and a unique randomization number will be sent by the CRO to the investigator soon after a copy of the inclusion and exclusion criteria will be fulfilled and signed by the investigator in the appropriate CRF form and sent by fax or email to the data management of the study CRO. Email address: [contact]. [contact].

Blinding

The investigators, the Sponsor, and any personnel involved in patients' assessment, monitoring and data management will be blinded to the patient assignment.

The active study drug and placebo will be packaged and labeled by Boehringer Ingelheim Company.

All study drugs blisters and tablets will appear identical to ensure blinding.

Study drugs will be dispensed by the site pharmacy, in accordance with the randomization code system and the blinded study team will have no access to study drug or placebo, or randomization information.

Emergency Identification of Study drug

In case of a medical emergency, when the study drug assignment is needed to make treatment decisions for the patient, the investigator may unblind the patient's drug assignment. The Sponsor and medical monitor should be notified of the event prior to breaking of the code, if possible. If this is not possible, the Sponsor should be notified immediately afterwards, and the patient's drug code assignment should not be revealed. The circumstances leading to the breaking of the code should be fully documented, in the investigator's study files and in the patient's source documentation. Treatment assignment should not be recorded in any study documents.

The reason for breaking the blind must be documented in the patient's CRF and in the patient's medical records.

Documentation of contact or attempted contact with the clinical research physician prior to breaking the blind must also be documented in the patient's medical records.

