8.4 Laboratory evaluations

Laboratory results will be reported to the investigator who will review abnormal laboratory findings for clinical significance. The investigator will document any laboratory test results that are clinically significant on the lab report and provide details of the relationship to investigational product and the action taken. If a change in a laboratory value represents a medical condition, the medical condition will be listed in the AE record unless this is a pre-existing medical condition allowed under the inclusion criteria. If no correlation is possible, the direction of change (increase or decrease) and the actual value will be recorded.

The institution will perform laboratory analyses according to the Visit Schedule (see [Table 2](#)). The sponsor must be provided with a copy of the laboratory's certification, and a tabulation of the normal ranges for each parameter required. Additionally, if at any time a patient has laboratory parameters obtained from a different outside laboratory, the sponsor must be provided with a copy of the certification and a tabulation of the normal ranges for that laboratory.

At any time during the study, abnormal laboratory parameters which are clinically relevant (e.g. require dose modification and/or interruption of study drug, lead to clinical symptoms or signs or require therapeutic intervention), whether specifically requested in the protocol or not, must be recorded on the appropriate Comment CRF page in addition to the appropriate laboratory CRF page. When abnormal laboratory values or test results constitute an adverse event (i.e., induces clinical signs/symptoms or requires therapy) they must be recorded on the Adverse Events CRF.

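### Post-randomisation dipstick glucose reaches the blinded investigator and can suggest the treatment, and in a crossover a period-1 reading suggests the treatment in both periods

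*Combined protocol and SAP*

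**What the plan says.** - **Mechanism.** Section 2.3 explains that the drug blocks renal glucose reabsorption "and thereby increases urinary glucose excretion".
- **Test.** Section 8.4.4 specifies a semi-quantitative dipstick "evaluation of glucose, protein, bilirubin, ketones, leukocytes and blood". On timing it says only: "Urinalysis will be performed according to the visit schedule".
- **Timing.** Table 2 (Section 4.2.1) carries the dipstick in footnote 3, under the safety samples taken at visits 1, 2, 3 and 5. That footnote gives its purpose as "urine dipstick for signs of infection and ketoacidosis". The lists in Section 4.2.2 for visits 2, 3 and 5 repeat the item: "Collect safety blood and urine samples. Including hematology and chemistry blood examinations and urine dipstick for signs of ketoacidosis or infection".
- **Recipient.** Section 8.4: "Laboratory results will be reported to the investigator who will review abnormal laboratory findings for clinical significance".
- **Blinding.** Section 4.3.2 says that the investigators, the sponsor and staff involved in assessment, "monitoring and data management will be blinded to the patient assignment". The safeguards it describes are identical tablets and blisters, pharmacy dispensing and restricted access to the code. None of them covers a laboratory result that reflects the drug's action.
- **Visit 3.** Section 4.2.2 heads it "Treatment washout visit (3) (day 56 ±7 days", in line with Table 2. The washout paragraphs of the synopsis and of Section 4.2 place the visit 3 tests at the end of the four-week washout.

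**The concern.** Identical tablets protect the blind only if no routine result shows which tablet was taken. Urine glucose is the direct expression of this drug's mechanism, and the plan reports it to the people it intends to keep blinded.

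The crossover widens the exposure. In a parallel trial a revealing result concerns one treatment. Here each patient takes both, so an inference about period 1 carries over to period 2 before period 2 begins. Past SGLT2 inhibitor exposure is an exclusion (Section 5.2), so the readings at visits 1 and 2 also give an off-drug comparison for the same patient.

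Several later steps depend on judgement:

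- the investigator assigns adverse event causality (Section 8.1.5), and drug-related events are summarised separately (Section 9.2.2);
- the investigator may stop treatment at discretion (Section 4.4.1), and a period-2 exit can remove a patient from the paired comparison in Section 9.2.1;
- concomitant therapy, including beta blockers, is broadly open (Section 6.2);
- EF and end diastolic diameter come from echocardiography at visits 3 and 5 (Sections 7.5 and 7.6), with no masked reading described.

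**Working it through.** **The plan's own figure.** The point disputes no stated number; 128 serves only as the denominator below. It reproduces. With SD of differences 40, difference 10, two-sided alpha 0.05 and power 0.80 (Section 9.1), N = (40 × (1.960 + 0.842) / 10)² ≈ 126 by normal approximation. At N = 128 a noncentral t calculation gives 80.1% power.

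**Is glucose measured on treatment?** Only Section 8.4.4 names glucose as an analyte, and it defers timing to Table 2. Table 2 has two candidate rows: the safety samples with the dipstick (visits 1, 2, 3, 5) and urine analysis for electrolytes (visits 2 to 5). Both include visits 3 and 5. By the day count in Table 2, visit 3 (day 56) ends period 1 and visit 5 (day 140) ends period 2. On the other placement of visit 3, its dipstick would follow four weeks of washout, and only visit 5 would be an end-of-treatment reading.

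**How much could one reading reveal?** The documents give no dipstick positivity rates, so these are assumptions: s = P(positive on drug), 0.90 to 0.99; f = P(positive on placebo), 0.10 to 0.70. The upper end of f is high because inclusion requires HbA1c of 7 to 12% (Section 5.1) and fasting glucose up to 240 mg/dL is admitted (Section 5.2). Allocation is 1:1, so prior odds are even.

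- Sequence correctly identified = 0.5 × (s + 1 − f)
- P(placebo given negative) = (1 − f) / [(1 − f) + (1 − s)]
- P(drug given positive) = s / (s + f)

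| s | f | Correct | Of 128 | Placebo given negative | Drug given positive |
|---|---|---|---|---|---|
| 0.90 | 0.70 | 0.600 | 77 | 0.75 | 0.56 |
| 0.99 | 0.70 | 0.645 | 83 | 0.97 | 0.59 |
| 0.95 | 0.30 | 0.825 | 106 | 0.93 | 0.76 |
| 0.90 | 0.10 | 0.900 | 115 | 0.90 | 0.90 |
| 0.99 | 0.10 | 0.945 | 121 | 0.99 | 0.91 |

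For example, 0.5 × (0.90 + 1 − 0.70) = 0.60 and 0.60 × 128 ≈ 77; 0.5 × (0.99 + 1 − 0.10) = 0.945 and 0.945 × 128 ≈ 121. Chance is 0.50, or 64 of 128. Across these rows a negative reading is at least as informative as a positive one, and usually more so.

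**Is the field needed?** Urine glucose appears in no endpoint (Section 4.1), no definition of an adverse event of special interest (Section 8.1.2) and no titration rule (Appendix 1, which uses blood glucose and HbA1c). The findings that Section 8.4.4 gives as examples prompting microscopy are leukocytes, nitrites and blood.

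**The case against.** The best counter-arguments, and what stands of each:

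- **The size is assumed.** This stands. A reader might infer that the blind is lost for most patients from visit 3 onward. The documents do not support that: they give no rates, and at 70% positivity on placebo one reading identifies only 60%.
- **Comparison with visit 2 need not sharpen the inference.** This stands in part. A patient already strongly positive off drug has little room to rise on a semi-quantitative strip, so no change does not point to placebo. Diabetes treatment may also change from visit 2 under Appendix 1. Patients negative at baseline remain easy to read.
- **Glucose may never be read.** Footnote 3 and the visit lists give infection and ketoacidosis as the purpose. That leaves Section 8.4.4 as the sole source, but it is explicit and nothing overrides it.
- **The primary endpoint is a device counter.** This stands. A reader might infer that the PVC comparison itself is biased. The route is only indirect: therapy changes, exits, the investigator's approval of device data, or recourse to Holter (Section 7.1). Knowledge gained at visit 3 cannot alter period-1 conduct, and the visit 5 reading comes after both treatment periods.
- **The echo consequence is inferred.** This stands. The documents do not say who reads the echocardiograms or whether that person sees the urinalysis, and Section 9.2.1 plans only summaries of these endpoints.
- **Other clues remain.** HbA1c is reported at visits 3 and 5, with a mean reduction of 0.7% cited in Section 2.2, and patients keep home glucose diaries. Masking one field does not restore a perfect blind, but it removes the most direct marker.

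**Conclusion.** The concern holds as a gap in the blinding provisions. Followed as written, the plan gives blinded staff a result that can suggest the treatment, and a period-1 reading suggests both periods. On assumed positivity of 90-99% on drug and 10-70% on placebo, one reading identifies the sequence in about 60-95% of patients (77 to 121 of 128), against 50% by chance. The range is an illustration, not an estimate from the documents.

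The early exposure depends on visit 3 falling at the end of period 1. Table 2 and Section 4.2.2 conflict with the washout paragraphs of the synopsis and Section 4.2, and these must be reconciled. Visit 5 is exposed on either placement.

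The risk falls mainly on causality assessment, discretionary discontinuation and concomitant therapy, and on EF and end diastolic diameter if the echo reader sees the result. For the PVC count it is indirect. The sample size and stated power are unaffected.

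**What to change.** Amend Section 8.4.4 and the blinding text of Section 4.3.2 to state that glucose on post-randomisation dipsticks is neither read by nor reported to blinded staff before database lock. The method depends on where strips are read, which the documents do not say:

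- if on site, use strips without a glucose pad after randomisation, since a laboratory report setting would have no effect;
- if in the laboratory, suppress the glucose field on released reports.

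Keep the other dipstick fields, including ketones, leukocytes, nitrites, protein and blood, and leave blood glucose and HbA1c monitoring unchanged. No masking rule is needed for glucose in the 24-hour or biobank urine, because the protocol does not say that such a result will be produced. Reconcile the two placements of visit 3 in the same amendment.

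The cost is a short amendment and either a strip choice or a report setting. Urinalysis is a listed safety assessment and laboratory data are CTCAE-graded (Section 9.2.2), so one safety-listed value is no longer visible to the site. With suppression it can be released after lock; with the pad omitted it is not collected. HbA1c and home glucose remain as weaker clues.

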8.5 Physical examinations/vital signs

A physical examination including vital signs will be performed according to the Visit Schedule (see [Table 2](#)). Information about the physical examination and vital signs must be present in the source documentation at the study site. Significant findings present prior to the start of study drug must be included in the Relevant Medical History/Current Medical Conditions CRF. Significant findings made after the start of study drug, which meet the definition of an adverse event, must be recorded on the Adverse Event Case Report Form. There are no Case Report Forms to capture routine normal findings from physical examinations and vital signs assessments. Vital signs will include body temperature (°C), respiratory rate (breaths/min), pulse rate (beats/min), systolic and diastolic blood pressure (mmHg).

9 Statistics

9.1 Sample size

The primary endpoint is the percentage of PVCs during the 2 months of empagliflozin treatment compared with the percentage of PVC on placebo. A sample size of 128 patients was selected based on the estimated effect of 10% reduction in the rate of arrhythmic events assuming a standard deviation of 40% in measured values, with alpha of 0.05 and power of 0.8 (2-sided test). The efficacy analysis will be conducted using an as treated approach and will be performed using the Wilcoxon signed-rank test, p value ≤ 0.05 will be considered significant.

The rationale for sample size calculation was based on detecting a difference of at least 10% in the reduction in rate of arrhythmic events from baseline between study treatments with 80% power and 5% significance level.

Sample size justification

When the sample size in each sequence group is 64, (a total sample size of 128) a 2 x 2 crossover design will have 80% power to detect a difference in Mean reduction of -10.0, assuming that the Crossover ANOVA MSE is 28.284 (the Standard deviation of differences, sd, is 40.0) using a two group T-test (Crossover ANOVA) with a 0.05 two-sided significance level.

Reference:

Senn, Stephen Cross-over Trials in Clinical Research (2nd Edition) Wiley (2002).

9.2 Efficacy and Safety evaluation

General

All measured variables and derived parameters will be listed individually and, if appropriate, tabulated by descriptive statistics.

For categorical variables, summary tables will be provided giving sample size, absolute and relative frequency and 95% CI (Confidence Interval) for proportions by study treatment.

For continuous variables, summary tables will be provided giving sample size, arithmetic mean, standard deviation, median, minimum and maximum and 95% CI (Confidence Interval) for means of variables by study treatment.

All tests will be two-tailed, and a p value of 5% or less will be considered statistically significant.

The data will be analyzed using the SAS ® version 9.3 (SAS Institute, Cary North Carolina).

Analysis Populations

Safety Population: will include all randomized subjects who received any study drug.

Intention-to-Treat (ITT) Population: will include all subjects included in the safety population who provided at least one post-baseline assessment for the primary endpoint.

Per-Protocol Population: will include all subjects in the ITT population who complete the study in compliance with the protocol and have no major protocol violations.

9.2.1 Efficacy analysis:

The primary endpoint is the percentage of PVCs during the 2 months of empagliflozin treatment compared with the percentage of PVC on placebo.

The two-sample T-test or Non-parametric Wilcoxon-Mann-Whitney Rank sum test for independent samples (as is appropriate) will be applied for testing the carry-over effect in the primary endpoint between the two sequences.

If no carry-over effect will be observed, then The Paired T-test or non-parametric Signed-rank test for two means (as is appropriate) will be applied for analyzing the difference in the above changes between the tested treatment and placebo.

Otherwise, if a carry-over effect will be found statistically significant, then the MMRM model (Mixed-effect model for repeated measures) will be applied for analyzing the difference in the above reduction between the tested treatment and the placebo. The model will included terms for study arm (sequence), treatment and period as fixed effects, and subject nested within study arm as a random effect. Other covariates (such as age and baseline measures) will be included if they will be found different between the groups and affecting the outcome.

Secondary Endpoints:

Frequency of non-sustained ventricular tachycardia (NSVT) episodes and composite cumulative ventricular arrhythmia load will be summarized by treatment.

Changes in blood level of NT-Pro Brain Natriuretic peptide (BNP), Left ventricular end diastolic diameter and Left ventricular ejection fraction (EF) from baseline will be summarized in appropriate tables by treatment.

9.2.2 Safety Analysis:

Data from all subjects who receive any study drug will be included in the safety analyses.

All adverse events will be coded using the Medical Dictionary for Regulatory Activities (MedDRA, most updated Version) terminology and presented in tables by System Organ Class (SOC) and Preferred Term (PT).

AE data will be listed individually and summarized by SOC and by PT within a system organ class under each treatment.

The severity of the toxicities will be graded according to the NCI CTCAE (Ver4.0) whenever possible. In the by-subject analysis, a subject having the same event more than once will be counted only once. Adverse events will be summarized by worst NCI CTC grade. Adverse events leading to death or to discontinuation from treatment, events classified as NCI CTCAE Grade 3 or Grade 4, study-drug-related events, and serious adverse events will be summarized separately.

Laboratory data will be graded according to NCI CTCAE severity grade.

Any deviations from the previously described statistical plan will be described and justified in a protocol amendment.

Other safety parameters including vital signs and physical examination will be summarized in appropriate tables.

Concomitant medications entered into the database will be coded using the World Health Organization (WHO) Drug Reference List, which employs the Anatomical Therapeutic Chemical classification system.

10 Direct Access to Source Data/Documents

Access to the subject's source data and study documents will occur only with the subject's acknowledgement and agreement by signing an informed consent. The investigator will permit study-related monitoring, audits, Institutional Review Board (IRB) review and regulatory inspection(s), providing direct access to source data and documents.

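### Sections 9.2 and 9.2.1 name confidence intervals only by treatment; the within-patient treatment difference should be reported with a period-adjusted 95% CI, and NT-proBNP as a within-patient ratio

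*Combined protocol and SAP*

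**What the plan says.** Section 9.2 (General) sets the reporting rule for continuous variables: sample size, then "arithmetic mean, standard deviation, median, minimum and maximum and 95% CI (Confidence Interval) for means of variables by study treatment". Categorical variables get a CI for each proportion, also by treatment. These are the only intervals that the plan names.

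For the primary endpoint, section 9.2.1 has two branches.
- No carry-over observed: "The Paired T-test or non-parametric Signed-rank test for two means (as is appropriate) will be applied for analyzing the difference in the above changes". No period term is mentioned. Section 9.1 names only one of these tests; the analysis "will be performed using the Wilcoxon signed-rank test, p value ≤ 0.05 will be considered significant".
- Otherwise: "if a carry-over effect will be found statistically significant, then the MMRM model (Mixed-effect model for repeated measures) will be applied", with terms for sequence, "treatment and period as fixed effects, and subject nested within study arm as a random effect".

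Neither branch names a point estimate or CI for the treatment difference. The sample size justification in 9.1, by contrast, assumes a two-group crossover ANOVA t-test.

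NT-proBNP is listed with the echocardiographic measures: "Changes in blood level of NT-Pro Brain Natriuretic peptide (BNP), Left ventricular end diastolic diameter and Left ventricular ejection fraction (EF) from baseline" are to be tabulated by treatment. No within-patient contrast and no scale are stated.

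**The concern.** In a crossover, both treatment means come from the same patients. A CI around each mean carries the full between-patient spread and ignores the pairing, so the two intervals side by side do not show how precisely the treatment effect is known. The design was chosen, and the sample size set, to use the within-patient difference; the planned tables do not commit to reporting it.

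The gap matters most if the primary test is not significant. A p-value above 0.05 does not separate a result that rules out the planning difference of 10 from one that leaves it open; an interval for the difference does.

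Two smaller losses follow the same pattern. The no-carry-over branch drops the period adjustment that the sizing assumed. NT-proBNP, one of the markers named in the secondary objective (3.2), has no planned treatment contrast at all.

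**Working it through.** **Inputs (section 9.1).** N = 128, 64 per sequence; SD of within-patient differences 40; difference 10; two-sided alpha 0.05; stated power 80%.

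**1. The plan's own figure.**
- SE = 40/sqrt(128) = 3.536. The two-group crossover form gives the same: half of 40 × sqrt(2/64) = 7.07/2 = 3.536.
- Power, normal approximation: Phi(10/3.536 − 1.960) = 0.807. Noncentral t with 126 df: 0.801.
- The stated 80% reproduces. The printed MSE of 28.284 equals 40/sqrt(2), so it is a root MSE.

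**2. The interval that the design supports.**
- Half-width = t(0.975, 126) × SE = 1.979 × 3.536 = 7.0.
- An observed −10 would be reported as −17.0 to −3.0.
- An observed −2 gives −9.0 to +5.0, which excludes −10. An observed −5 gives −12.0 to +2.0, which does not. Both are non-significant, yet they mean different things.

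**3. What by-treatment intervals show instead.** Assume equal variances and within-patient correlation rho (not in the documents).
- Per-treatment SD = 40/sqrt(2(1 − rho)).
- The ratio of unpaired to paired width is 1/sqrt(1 − rho), whatever the SD.

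| rho (assumed) | SD per treatment | CI of each mean | Unpaired CI of difference | Ratio to ±7.0 |
|---|---|---|---|---|
| 0 | 28.3 | ±4.9 | ±7.0 | 1.0 |
| 0.3 | 33.8 | ±5.9 | ±8.3 | 1.2 |
| 0.5 | 40.0 | ±7.0 | ±9.9 | 1.4 |

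At a difference of 10 and rho = 0.5, the two by-treatment intervals overlap (7.0 + 7.0 > 10), although the paired interval excludes zero.

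**4. Period.** Let Delta be the period 1 minus period 2 effect, and n1, n2 the numbers completing each sequence. The simple mean of the empagliflozin-placebo differences estimates the treatment effect plus Delta × (n1 − n2)/(n1 + n2).
- At 64/64 the added term is zero, but the variance of the differences rises from 40² to 40² + Delta². For an assumed Delta of 10, the SD is sqrt(1600 + 100) = 41.2 and the half-width about 7.2.
- Withdrawn subjects are not replaced (4.4.1), so balance is not guaranteed. If one sequence lost 8 patients and the other none (assumed), the bias would be 8/120 = 0.07 of Delta.
- Both effects are small here; the adjustment removes both.

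**5. NT-proBNP, illustration only.** Assumed: log-normal values, log-SD 0.8 to 1.2, within-patient correlation 0.8 to 0.9, true ratio 0.85, 128 patients, 4,000 simulated trials per setting. A paired t-test has power 0.30 to 0.96 on raw differences and 0.67 to 1.00 on log differences; at log-SD 1.0 and correlation 0.8, 0.49 against 0.82. A second set of assumptions (between-patient log-SD 0.8 to 1.2, within-patient 0.3 to 0.4, a 12% fall) gives 29 to 71% against 71 to 94%. The plan contains no such test, and the advantage follows from the assumed skew.

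**The case against.** The strongest reply is that the comparison itself is paired, and nobody proposes to combine the two by-treatment intervals.
- **The CI is partly recoverable.** In the paired t branch, the two means (on the same pairs) and the p-value determine the SE and hence the CI. This stands. It fails in the signed-rank branch, which is the test that 9.1 names.
- **A reader might infer that 9.2.1 contains nothing but tests.** It does not: the mixed model can yield a treatment difference and CI. However, it is used only after a significant carry-over test, and its estimate and CI are not named.
- **The summaries are not means alone.** The median, minimum and maximum are listed too, and 9.2 is hedged: "All measured variables and derived parameters will be listed individually and, if appropriate, tabulated by descriptive statistics". This softens the point on skew, but these summaries are also by treatment.
- **A reader might push rho to 0.8 or 0.9 and quote much larger ratios.** With an SD of differences of 40, those values need per-treatment SDs of 63 and 89, which a burden between 0 and 100% cannot have.
- **A reader might infer that NT-proBNP is tested on the raw scale and that a few patients will dominate the result.** The plan only summarises it, the raw scale is inferred from silence, and nothing in the documents describes its distribution.

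**Conclusion.** The point holds as a free improvement. The plan names no estimate or CI for the within-patient treatment difference in either branch, omits period when no carry-over is observed, and gives NT-proBNP no within-patient contrast.

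The one size that rests on the plan's own inputs is the ±7.0 half-width. The 1.4 ratio also needs the assumed correlation of 0.5, and the NT-proBNP gain needs right skew. The sample size is not in question, since the 80% power reproduces.

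One condition attaches to any statement that 10 is excluded. Section 9.1 speaks of a 10% reduction in arrhythmic event rate and of a mean reduction of −10.0, while the primary endpoint is PVCs as a percentage of all beats. The interval and the planning difference must be on the same scale before they are compared.

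**What to change.** In section 9.2.1, before unblinding:
- State that the primary result is the period-adjusted within-patient empagliflozin-placebo difference with its 95% CI, on the scale of the primary endpoint, and express the planning difference on that scale.
- Name the estimator for each branch: the crossover ANOVA (two-group) difference for the t-test; the Hodges-Lehmann estimate and CI for the rank test (period-adjusted: half the shift between sequences in period 1 minus period 2 values); the LS-mean difference and CI for the mixed model.
- Analyse NT-proBNP on the log scale within patient, adjusted for period, and report the empagliflozin/placebo geometric mean ratio with 95% CI. The end-of-period values at visits 3 and 5 suffice; a single visit 2 baseline cancels from the contrast.
- Keep the by-treatment tables as description.

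The cost is SAP wording, recorded by protocol amendment as 9.2.2 requires, and a little programming. No new data, visits or patients are needed.
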